- (1) Investigate the status of ER α -p53 interaction in ER α -positive, p53-wild type breast tumors in untreated patients and examine how tamoxifen therapy modifies this interaction in relation to existing estradiol and estrone levels.
- (2) Confirm the wild type status of p53 and analyze the functional status of p53 pathway by monitoring expression of selected p53-target genes in tumors in patients who have or have not been treated with tamoxifen.

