This is a multiple institute study coordinated by Roswell Park Cancer Institute Network Office. See Appendix 2 for Network specific information.

Women will present to the University of Chicago Medical Center (UCMC) Breast Center and Roswell Park Cancer Institute (RPCI) breast center with either an abnormal mammogram, new discrete breast mass, or biopsy proven cancer. Those women with abnormal mammograms (BRIRADS 4 and 5) or suspicious masses will undergo a diagnostic core biopsy after being evaluated in the breast center, the intake point of all new breast cases through the surgical clinic. Once an invasive carcinoma is confirmed on core biopsy by our staff pathologist, the majority of women will undergo definitive surgery to remove the tumor and determine staging. Typically, at University of Chicago and RPCI the interval between biopsy and definitive surgery is between two-four weeks. To examine the interaction between ER α and P53 with and without tamoxifen unfixed tumor tissue (fresh or frozen) is needed. A pilot randomized trial is proposed in ER α positive women to study this interaction. ER α positive disease will be identified at their initial visit, or upon return to the clinic to discuss core biopsy results. A p53 staining will be performed on the diagnostic core biopsy if an ER α positive malignancy is identified (Allred score of 3 or higher). The results of the p53 status will not be used for eligibility. ER/PR/HER-2 analysis of the diagnostic core biopsy tissue is done routinely as a standard of care. Women with tumors which are ER α positive will be enrolled if they meet eligibility criteria. Women will either be randomized to standard of care surgical therapy or a four week intervention prior to surgery; Based on our preclinical studies four weeks of tamoxifen exposure is adequate to study the interaction between ER α , p53 and tamoxifen in the tumor tissue. During the intervention, blood will be drawn from the participants to measure levels of tamoxifen metabolites in the blood and test for polymorphisms that may decrease levels of active metabolites. Estradiol and estrone levels in the blood and tumor tissues of all patients with or without intervention will be measured.

Eligibility Criteria:

Inclusion Criteria:

- (a) The patient must consent to be in the study and must have signed an approved consent form conforming to institutional guidelines
- (b) The patient must be 18 years or older.

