An initial blood draw for PK/PD studies will be done prior to starting tamoxifen. There will be no PK/PD samples for patients randomized to the observation arm. Pre-dose, 2 green top tubes are to be obtained followed by 1 green top tube of blood for all other samples are to be obtained for PK/PD studies for each time point noted in the Study Schedule (Appendix 1). Once patients are enrolled, they will be seen by the study nurse one time prior to their surgical date at which time they will undergo adverse events assessment. During this appointment, patients will undergo standard of care pre-operative blood work. One additional tube of blood will be obtained from the patient at this time to measure the levels of tamoxifen and tamoxifen metabolites in the blood.

Patients at RPCI must be enrolled in the RPCI DBBR protocol (I 03103) to participate in this study. The DBBR will obtain blood for banking as per standard DBBR protocol. DBBR samples will be drawn prior to surgery. At the completion of the study, the DBBR will provide DNA for polymorphism studies. At the University of Chicago, one EDTA (purple or pink) tube of blood will also be collected for polymorphism studies from all patients participating in the study. At the conclusion of the study the research nurse will do toxicity assessments post tamoxifen, on the day of surgery. An additional tube of blood will be needed for PK/PD studies.

All blood samples collected in this study will be processed and stored at -70 until being shipped via dry ice (overnight delivery) for analysis. Plasma will be separated from the total blood within 30 minutes following the extraction. Shipments should be to the attention of Roswell Park Cancer Institute, Bioanalytics, Metabolomics and Pharmacokinetics (BMPK) Shared Resource, [name], [name], e-mail address: [contact]. For additional information regarding the handling of pharmacokinetic samples please contact RPCI's BMPK Shared Resource at [contact]. Batch shipment every 2-3 patients is preferred. Shipment should only occur Monday-Thursday's.

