PK/PD analysis will be under the supervision of the Director of the Bioanalytics, Metabolomics and Pharmacokinetics (BMPK) Shared Resource facility at RPCI. Two tubes of blood, 10 ml each, will be drawn 0-30 days prior to the first dose of tamoxifen for PK sampling, estradiol and estrone analysis (tube 1), and genotyping (tube 2), and an additional PK sample of one tube at week 2 or 3 after receiving tamoxifen. An additional PK sample will be collected for all patients on the day of surgery. Also, a core tissue biopsy will be collected at the time of surgery to assess the concentration of tamoxifen and its active metabolites, as well as estradiol, in the surrounding breast tissue. Blood drawn prior to tamoxifen administration will be used to calculate the genotype of CYP2D6 and 3A4/5 and also to ensure tamoxifen levels are zero, and to measure the estradiol concentration. The other 2 samples (2 samples in duplicate) will be used to measure plasma and tissue concentrations of both TAM and its metabolites in comparison to estradiol and estrone concentrations by assessing (a) the area under the curve (AUC; $AUC_{\text{tamoxifen}}$, $AUC_{4\text{-OH-tamoxifen}}$, $AUC_{\text{N-desmethyl-tamoxifen}}$, and $AUC_{\text{endoxifen}}$ and the corresponding metabolic ratios), (b) clearance (CL) of TAM ($CL_{\text{tamoxifen}}$), and (c) maximal concentrations (C_{max}) of TAM and its metabolites. With the 2 time points, a population PK model will be built and then used to estimate individual AUCs or CL. With the 2 time points, a population PK model will be built and then used to estimate individual AUCs or CL. These measurements, as well as the observed C_{max} , will then be tested for association with genotype and baseline estradiol concentrations. Demographic and clinical data (ethnicity, current age, age at diagnosis, menopausal status) will be collected for these patients. Samples of blood (10 ml) will be collected in heparinized tubes centrifuged at 4° C and plasma is stored frozen at -70 °C or lower until analysis by LC/MS/MS. Derivation of PK parameters and modeling is described below.

PK/PD Modeling:

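### Estradiol and estrone are promised in blood and tumor of every patient, but the sampling rules contradict each other on control-arm blood and give tumor no hormone assay step

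*Combined protocol and SAP*

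**What the plan says.** Objective 1, at the start of the protocol, is in part to "examine how tamoxifen therapy modifies this interaction in relation to existing estradiol and estrone levels". The Study design text in Section III gives the matching commitment: "Estradiol and estrone levels in the blood and tumor tissues of all patients with or without intervention will be measured".

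The sampling instructions differ.

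- **Section IV, blood.** "There will be no PK/PD samples for patients randomized to the observation arm". The calendar in Appendix 1 agrees: its PK/PD blood row is for the tamoxifen arm only, at all three draws.
- **Section V, PK/PD studies.** The pre-dose blood is to be drawn "prior to the first dose of tamoxifen for PK sampling, estradiol and estrone analysis (tube 1), and genotyping (tube 2"), so the hormone assay belongs to a PK tube timed from a drug that controls never take. The same paragraph adds: "An additional PK sample will be collected for all patients on the day of surgery". It says that the post-dose samples "will be used to measure plasma and tissue concentrations of both TAM and its metabolites in comparison to estradiol and estrone concentrations".
- **Which hormones.** Tube 1 is for both. Later in the paragraph the same pre-dose blood serves "to ensure tamoxifen levels are zero, and to measure the estradiol concentration", with estrone dropped. The PK measures will "then be tested for association with genotype and baseline estradiol concentrations".
- **Tissue.** Section IV assigns both hormones to a core of surrounding normal breast. The PK/PD studies text names only estradiol for that core. The calendar's core-biopsy row names no hormone.

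**The concern.** A coordinator who works from Section IV and the calendar will draw no hormone blood from any control, and blood not drawn before treatment or at surgery cannot be recovered. One who works from the PK/PD studies text will draw a surgery-day tube from everyone. If the two sites follow different passages, the control hormone data that exist will depend on site.

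At stake is the estrogen part of Objective 1. How tamoxifen's effect on the interaction varies with hormone level is a between-arm question, so it needs hormone levels in both arms at comparable times. With blood from one arm only, what remains is a correlation among treated patients.

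**Working it through.** The plan states no figure for this point, so the check sets the passages side by side and then counts the patients affected.

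| Place | Blood from controls | Hormone assay in tissue |
|---|---|---|
| Section III, Study design | Both hormones, every patient | Tumor, every patient |
| Section IV | No PK/PD blood; banking or polymorphism blood only | Surrounding normal breast, both hormones |
| Section V, PK/PD studies | Hormone tube timed from first tamoxifen dose; surgery-day PK sample from everyone | Surrounding breast, estradiol only |
| Section V, tumor procedures | Not applicable | ChIP, PLA, IHC, sequencing and qRT-PCR; no hormone assay |
| Appendix 1 calendar | PK/PD row tamoxifen arm only; DNA row both arms | Core row lists tamoxifen, metabolites and future pharmacogenomics; no hormone |

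**Blood.** Rows 1 and 3 cannot both be met if rows 2 and 5 are obeyed. Reading hormone blood as something other than PK/PD blood does not help, because the only tube expressly assigned to the hormones is a PK tube; no separate hormone tube is scheduled for controls. Plasma might be left over from the Chicago EDTA tube, since Section IV has plasma separated from study blood, but no step assigns it to a hormone assay. What the RPCI bank stores is set by a protocol outside these documents.

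**Tissue.** Tumor levels are promised in row 1, but no procedure or calendar row in the visible text carries out the assay.

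**Patients affected.** Inputs: 50 patients (Section IV, Enrollment) and blocks of 4 (Section VI, Randomization). The allocation ratio is not stated.

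- *If 1:1 (2:2 within blocks), one list:* 50 = 12 × 4 + 2. Controls = 12 × 2 = 24, plus 0 to 2 from the incomplete block, so 24-26.
- *If 1:1, one list per site:* the leftovers at the two sites are (0, 2), (1, 1) or (3, 3). The first two give 24 plus 0 to 2. The third gives 11 × 2 = 22, plus 1 or 2 at each site. The range is again 24-26.
- *If the 28-30 tamoxifen-treated women to be genotyped (Section III, polymorphisms text) are the treated arm:* 50 − 30 = 20 and 50 − 28 = 22, so 20-22 controls.

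Across these assumptions 20-26 of 50 patients, or 40% to 52%, have no blood designated for hormones under Section IV and the calendar. For tumor, the missing step concerns all 50.

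**The case against.** **The control tube is there.** The PK/PD studies text draws surgery-day blood from everyone and compares drug levels with both hormones. A control has no tamoxifen to measure, so a hormone assay is the sensible purpose of that tube. This is a fair inference. It leaves the conflict with Section IV and the calendar over whether the tube is drawn at all, and it supplies no pre-treatment level.

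**It carries little weight.** The summary restates Aim 1 without the hormone clause. The Background says only that disruption of the interaction may be further correlated with estrogens. Section VI specifies no estradiol or estrone analysis and does not name the hormones among its adjustment factors. All of this stands and limits the point to an exploratory analysis in a pilot.

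**The text is incomplete.** The PK/PD Modeling paragraph breaks off mid-sentence in the copy reviewed. The statement about tumor is therefore confined to the visible text.

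A reader might also infer more than the documents support:

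- *That tumor hormones are not planned.* The Study design text plans them; the operational step is what is missing.
- *That controls would have no hormone data at all.* The normal-breast core is not restricted by arm.
- *That surgery-day blood alone would do, because ChIP is run on resected tumor.* Objective 1 speaks of *existing* levels, most naturally those before tamoxifen, and the protocol puts the hormone assay in a pre-dose tube. After four weeks of drug, a surgery-day level is a post-treatment covariate.

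**Conclusion.** The plan contradicts itself and should be corrected. As written, Section IV and the calendar defeat the Study design commitment on control blood, the PK/PD studies text conflicts with both on the surgery-day sample, and the tumor part of the commitment has no operational step in the visible text.

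If Section IV and the calendar are followed, the blood-hormone part of Objective 1 cannot be compared between arms. About half of the 50 patients are affected if allocation is 1:1, or 20-22 if the 28-30 women are the treated arm. The counts take 50 as the final total; unevaluable patients are replaced, and the documents do not say whether replacements fall within the 50.

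It would be wrong to conclude that the primary result is at risk. The Fisher comparison of ChIP/PLA positivity and its stated power use no hormone data. A correlation within the tamoxifen arm remains possible, as do normal-breast levels in both arms and a later tumor assay if frozen tissue remains.

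**What to change.** Reconcile the Study design text, Section IV, the PK/PD studies text and the calendar.

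1. **Blood.** Limit the Section IV exclusion and the calendar's PK row to tamoxifen and metabolite sampling. Add a calendar row for estradiol and estrone blood in both arms at the same time points: a pre-treatment tube, which gives a covariate free of treatment effect, and the surgery-day tube that the PK/PD studies text already calls for. State that both hormones are assayed at each.
2. **Tissue.** Either assign a frozen tumor aliquot to the hormone assay where tissue remains after ChIP, qRT-PCR and sequencing, or limit the Study design commitment to surrounding breast. Make Section IV, the PK/PD studies text and the calendar's core-biopsy row name the same hormones.
3. **If control blood is not wanted.** Restrict the blood commitment and the blood-hormone part of Objective 1 to the tamoxifen arm, and remove the all-patients wording from the surgery-day sentence.

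Options 1 and 2 need a wording and calendar amendment. Control blood costs one or two tubes per control: 20-26 tubes at one each, or 40-52 at two each, over the range of control counts above. A tumor aliquot competes for limited tissue, so it should come after the other tumor assays. Option 3 costs wording only but gives up the between-arm blood-hormone comparison.

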Standard surgical therapy will be offered to the patient based on the size, location of their tumor or presence of multiple tumors. After the completion of the surgical resection, two core biopsies of the surrounding normal breast tissue will be taken. One will be used to evaluate for tamoxifen and tamoxifen metabolite levels as well as estradiol and estrone levels in the breast tissue. The second will be stored for future pharmacogenomic studies.

Sequential compression devices (SCD's) will be used as part of standard of care for all women undergoing general anesthesia. Even though there is no data to suggest that a short intervention with tamoxifen will increase the risk of thrombosis, only women who get the tamoxifen arm will receive 5000u of subcutaneous heparin in the pre-operative holding area in addition to the use of SCD's for added prophylaxis.

Patients will undergo adjuvant therapy according to the findings of their surgical pathology. If the patient undergoes Oncotype testing as part of their standard of care, we will collect that information as part of our clinical data for analysis.

ENROLLMENT: Patients would be enrolled in this study at both the University of Chicago and the multidisciplinary breast clinic at RPCI. We plan to accrue 50 patients to this study over 9-year study duration. Anticipated rate of accrual would be 2-3 patients a month.

Tamoxifen is commercially available as a 20 mg tablet. The appropriate grant supporting the study will pay for the tamoxifen and will be provided free-of-charge to patients enrolled in this study.

V. REQUIRED STUDIES

Collaborating institutional staff pathologist will supervise all pathology examinations.

Estrogen Receptor, Progesterone Receptor And Her2 Expression Status:

Biopsy specimens: Estrogen and progesterone receptors are critical for inclusion in this protocol and should either be available as a part of routine analysis or will be done as a part of screening for this study in patients otherwise eligible for the study. Enrollment in the study will be predicated on the presence of ER based on an Allred score of 3 or above. The results of the p53 status will not be used for eligibility and will be determined at the end of study. HER2 expression status is not required prior to accrual.

Genotyping:

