We have been successful with ChIP assays in both fresh and recently frozen mouse tissues. If a patient consents to fresh tissue collection and the tissue procurement resource contains insufficient sample to release for testing, this testing will not be required. The frozen tissue from the University of Chicago will be sent via FedEx on dry ice the same day to the laboratory of [name] at Roswell Park Cancer Institute [name]. If the surgical sample is harvested on Friday, it will be stored at -70 over the weekend and shipped on Monday morning. In addition, PLA for protein-protein interaction will be performed in [name] laboratory on unstained slides of tumor specimens provided by [name] (Department of Pathology, RPCI). Similarly, PLA will be performed on unstained slides of tumor specimens sent (by FedEx, overnight) from University of Chicago to the laboratory of [name] at RPCI.

Determination of p53 sequence in tumor samples:

All evaluations will be done blindly in the absence of any identifying information from IHC as to the intensity of p53 staining. Various studies have indicated that IHC by itself may not be a reliable method to determine p53 status in tumors. As explained above, IHC determination is based on the assumption that mutant p53 is more stable leading to higher signal in IHC. However, that is not always the case. For example, 20% of tumors with a mutant p53 did not show nuclear accumulation of the protein (2). Sequence determination of p53 gene is more precise in determining wild

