First, we will analyze if ER α -p53 interaction in tumors affects p53's function as a transcriptional regulator. Toward this goal, we will analyze a selected group of p53-target genes (based on their reported importance in regulating cell cycle and apoptosis (63,64) that are either activated or repressed by p53 in the resected tumor tissue. . ***We have already demonstrated that Survivin (whose transcription is known to be repressed by p53) expression is upregulated as a consequence of ER binding to p53, and treatment with TAM leads to functional activation of p53, thereby restoring p53's ability to repress Survivin expression (65).*** The mRNA levels of these genes will be analyzed by qRT-PCR, a technique routinely used in the PI's laboratory. Subsequently, we will analyze the expression of these genes at the protein level. Immunohistochemistry (IHC) studies of these proteins will be conducted in the core biopsy samples (unstained slides will be requested for biopsies performed outside RPCI) and surgically excised tumor tissue of the study subjects using a tissue microarray (TMA) generated by the Department of Pathology under the supervision of [name]. For patients recruited at the University of Chicago, TMA will be generated at the University of Chicago. IHC will be performed under the direction of the pathologist, with all pathology personnel blinded to treatment assignment. The IHC endpoints will be rounded to the nearest 10% by the pathologist who will be blinded to the treatment group assignment. The ER and p53 status will be determined as described in the earlier section (section 4.1.1). Staining for p21, Bax, puma and Survivin will be evaluated qualitatively and scored on a 0 – 3+ intensity scale (0 = negative staining, 1+ = weak staining, 2+ = moderately intense staining, and 3 + = strong staining. It is to be noted that p53-target gene protein expression will be analyzed by IHC both in the core biopsy samples and surgically excised tumor tissue enabling within-patient comparison of expression profile of these proteins *before* and *after* TAM therapy. Ideally, a similar within-patient approach is desirable for other assays (ChIP and qRT-PCR,) as well. However, it is practically impossible given the limited tissue availability from the pre-surgical biopsy.

VI. STATISTICAL CONSIDERATIONS

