The bio-statistician at RPCI will perform the statistical analyses and aid in interpretation of results. Exploratory graphical analysis and data confirmation will precede formal inferential analysis. As this is an investigational study, no correction for multiple testing will be made; p-values less than $\alpha=0.05$ will be deemed statistically significant. While formal power computations are provided, it is expected a larger Phase III trial will be planned to confirm and elaborate promising findings. The demographic and baseline data will be summarized by treatment group. Descriptive statistics such as frequencies and relative frequencies will be computed for all categorical variables. Numeric variables will be summarized using simple descriptive statistics such as mean, standard deviation, quartiles, etc. Ninety-five percent confidence intervals will be computed when appropriate. A variety of graphical techniques will be used to display data.

The primary analyses in Aim 1 are comparisons of ER α -p53 interaction (positive or negative) between independent treatment and control groups. The proportions of patients with positive ChIP assay/PLA will be compared with Fisher's Exact Test, which has 80% power to detect a difference of about 0.41 between the two group; e.g., a difference of 70% in the control group vs. 30% in the TAM group. In Aim 2, mean mRNA levels, as measured by qRT-PCR, will be compared across treatment and control groups. The difference in log fold intensity between treatment and control will be estimated with an independent samples t-confidence interval. The corresponding hypothesis test has

80% power to detect an effect size of 0.91. That is, if the true difference in means is about 0.91 standard deviations, there is an 80% probability our study will correctly reject the null hypothesis of no effect.

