Protein expression measured by IHC gives an ordinal variable (0, 1+, 2+, 3+). For each protein, the four-week intensity change ("post – pre" will be between -3 and 3) will be compared between treatment and control groups with the Wilcoxon-Mann-Whitney test. In the control group we expect little change because no treatment has been given between samples. For power calculations we assume 80% of patients in control will have no change and 10% will increase and decrease. As a hypothesis, we estimate half of patients in the treatment group will have no change and the rest will increase one (e.g. from 1+ to 2+) or two categories (e.g. from 1+ to 3+). From simulation we estimate the power to correctly reject the null hypothesis when this alternative is true is about 90%.

It is possible the response variables in Aims 1 and 2 are correlated with clinical factors such as patient age, smoking status, and position in menstrual cycle. Additional exploratory comparisons of response between treatment and control groups will be made after adjustment for clinical factors with linear or logistic regression as appropriate. These secondary analyses may have greater ability to detect a treatment difference by controlling variability unrelated to treatment. PK/PD data modeling was described previously. Pharmacogenomic data will be explored with the general linear model $Y = a + bG + e$, where genotype G is quantified 0, 1, 2 for aa , Aa , AA , respectively; for quantitative response Y , normal linear regression is used; for binary response, logistic regression is used.

Randomization:

Patients will be allocated to treatment or control by block randomization (block size=4). The randomization assignment list will be maintained at RPCI. The nurse/coordinator from University of Chicago will notify the RPCI Network office for a randomization assignment by sending the completed patient registration form to [contact]. The Network Monitor or designee will randomize the patient and send the randomization assignment to the nurse/coordinator at University of Chicago.

Management of Patients After Completion of Tamoxifen Treatment:

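### The main comparisons leave out site although the two sites ship tissue and build microarrays differently; this costs precision and exposes the trial to chance imbalance, but does not bias the tests

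*Combined protocol and SAP*

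**What the plan says.** **Sites and size.** Section IV (Enrollment) says "Patients would be enrolled in this study at both the University of Chicago and the multidisciplinary breast clinic at RPCI", and "We plan to accrue 50 patients to this study over 9-year study duration". It gives neither the expected split between sites nor the number per arm.

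**Tissue paths (Section V).** "The frozen tissue from the University of Chicago will be sent via FedEx on dry ice the same day", with Friday specimens held at -70 until Monday. RPCI frozen tissue goes straight to the same laboratory. Chicago slides for the proximity ligation assay (PLA) are also couriered to RPCI. For the tissue microarrays (TMAs), "For patients recruited at the University of Chicago, TMA will be generated at the University of Chicago"; the others are made by the pathology department at RPCI.

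**Allocation.** Section VI (Randomization) and Appendix 2 (item 3) both describe permuted blocks of 4 and add "The randomization assignment list will be maintained at RPCI". Neither names a stratification factor.

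**Analysis (Section VI).**
- ChIP/PLA positivity is compared by Fisher's exact test, "which has 80% power to detect a difference of about 0.41 between the two group".
- mRNA is compared by an independent-samples t interval, with 80% power for 0.91 SD.
- The change in immunohistochemistry (IHC) score is compared by Wilcoxon-Mann-Whitney.

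None of the three includes site. Covariate adjustment is exploratory. Its examples are age, smoking and menstrual-cycle position, and site is not among them.

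**The concern.** All three between-arm tumour comparisons use material whose path depends on site. Shipping affects the frozen tissue used for ChIP and qRT-PCR. TMA construction affects IHC and PLA. ChIP and qRT-PCR have no pre-treatment sample, as Section V itself explains, so a within-patient difference cannot remove a site effect. For IHC, the difference cancels whatever is common to both samples. It does not cancel a TMA effect, because the earlier sample is the core biopsy and the later one sits on a site-built array.

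If site does shift these readouts, two things follow. The shift adds to the residual variance of an unadjusted test. And in a trial of 50, one arm can by chance hold noticeably more Chicago patients, which moves the estimate in the one trial actually run. Section VI expects promising findings to lead to a larger trial, so the precision of this estimate matters.

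**Working it through.** **Inputs from the documents.** N = 50, taken as 25 per arm; blocks of 4; two sites; alpha 0.05, with two-sided testing assumed; ChIP/PLA 70% vs 30%; mRNA effect 0.91 SD.

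**Assumed, because the documents do not give them.** Chicago share p of 30-50%; site shift s of 0 to 1.5 within-site SD for mRNA; relative loss of ChIP/PLA positivity at one site of 0-40%.

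**1. The plan's own figures.** Exact enumeration of Fisher's test at 25 per arm gives 80.5% for 70.5% vs 29.5% and 78.2% for 70% vs 30%. The stated 80% for a difference of about 0.41 is reproduced. For 0.91 SD, the noncentral t gives 80.1% at 20 per arm and 88.3% at 25 per arm. The mRNA figure therefore fits 20 per arm, and results for both sizes are shown in step 3.

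**2. Chance imbalance.** The difference D between the arms' Chicago shares has SD of about sqrt(p(1-p) × (1/25 + 1/25)):
- p = 0.5: sqrt(0.25 × 0.08) = 0.141, so mean |D| is about 0.80 × 0.141 = 0.11.
- p = 0.3: sqrt(0.21 × 0.08) = 0.130, so mean |D| is about 0.10.

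Simulating one list of blocks of 4 gives a mean of 10-11 points and at least 20 points in about 15-19% of trials. At p = 0.5, D reaches 28 points or more in about 6%. With site-stratified blocks the mean is about 2 points, and 20 points was not reached.

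**3. mRNA.** The unadjusted test sees an SD of sqrt(1 + p(1-p)s²), so the standardized effect is 0.91 divided by that value. At p = 0.5:

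| s | SD seen | effect | power, 25/arm | power, 20/arm |
|---|---|---|---|---|
| 0 | 1.000 | 0.910 | 88% | 80% |
| 0.5 | 1.031 | 0.883 | 86% | 78% |
| 1.0 | 1.118 | 0.814 | 80% | 71% |
| 1.5 | 1.250 | 0.728 | 71% | 61% |

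At p = 0.3 and 25 per arm the last three rows are 87%, 82% and 74%. Simulation agrees within about a point. Adding site to the model while keeping the single list holds power at 87-88% for 25 per arm. Stratifying allocation as well gives 88-89%.

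**4. ChIP/PLA, 70% vs 30%, N = 50 (simulated).**

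| Loss at one site | Fisher | Site-stratified exact |
|---|---|---|
| 0 | 78% | 78% |
| 20% | 68-73% | 71-74% |
| 40% | 59-67% | 61-68% |

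The recovery is about 1-3 points. Most of the loss comes from the lower positivity itself, which no analysis restores.

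**5. Type I error.** Over all randomizations the unadjusted t-test rejects in about 5% and Fisher in 2.5-3.5%. In the trials with at least 20 points of site imbalance, the t-test rejects a true null in about 10% at s = 1 and 14-15% at s = 1.5. This is offset by rates below 5% in the others. Stratifying allocation without adjusting makes the t-test conservative (about 3% at s = 1).

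**The case against.** **A reader might infer bias or inflated error.** The documents do not support that. Allocation is random, so site is balanced in expectation and overall type I error holds. A distortion of 6-8 points in the ChIP/PLA difference can be obtained, but only by multiplying a tail imbalance (28 points, about 6% of trials) by an assumed 20-30 point site effect. At the average imbalance the product is 0.11 × 20-30, about 2-3 points. The standard error of the difference is sqrt(2 × 0.21/25), about 13 points.

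**The power loss depends on what SD means.** Section VI does not say whether 0.91 is in within-site or pooled units. If pooled, site variance is already included and the stated power stands; adjustment is then a gain forgone, not a shortfall. This objection stands.

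**Handling is largely common.** Both sites transport on ice, aim for receipt within 30 minutes and freeze to -70. Frozen tissue and PLA slides converge on RPCI, and IHC readers are blinded to arm. TMA construction does not touch ChIP or qRT-PCR. This narrows the plausible site effect but does not remove the shipping and array differences.

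**Separate site lists have a price.** Treatment is unblinded and the block size is printed in the site instructions. Guessing the under-represented arm succeeds about 54% of the time when a site sees its half of a common list, and about 70% with its own fixed blocks of 4. This also stands and shapes the fix.

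**It is a pilot with an open covariate list.** That is true, but the list covers clinical factors and is exploratory only.

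**Conclusion.** The point holds as one of efficiency and of protection against chance imbalance. No planned main test includes site, although site determines part of the tissue path. The exposure is a site-share difference of about 11 points on average and at least 20 points in about 15-19% of trials of 50. For mRNA at 25 per arm, the loss from about 88% is 1-2 points at a 0.5 SD shift, 7-8 at 1 SD and 14-17 at 1.5 SD, and a site term recovers nearly all of it. For ChIP/PLA the power gain is small, and the benefit is mainly protection against an unlucky split.

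These figures are a sensitivity range. They rest on an assumed site split, an assumed site effect and a within-site reading of the 0.91 SD; if the site effect is small, little is lost. The absence of stratification is inferred from silence in both randomization sections. The point does not extend to pharmacokinetics, which is sampled in the tamoxifen arm only, or to genotyping, which is not a between-arm efficacy test.

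**What to change.** In Section VI, pre-specify site in the main analyses:
- mRNA: linear model with arm and site.
- ChIP/PLA: site-stratified exact test.
- IHC change: site-stratified rank test (van Elteren).

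In Section V, require both arms on every TMA and in every assay batch. For Chicago-built arrays this means mixing arms within each array.

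Stratifying allocation by site is optional, since adjustment alone on the existing list recovers nearly all the mRNA power. If it is done, use varying, undisclosed block sizes, remove the block size from the site instructions, and keep site in the analysis so that the t-test does not become conservative. Because unevaluable patients are replaced, stratified allocation would not guarantee site balance among those analysed, which is a further reason to rely on the analysis.

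The cost is a few lines of text, one degree of freedom, and at most about 1-2 points of power if there is no site effect. The analysis change can still be made after enrolment has begun, provided it is fixed before outcome data by arm are seen.
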